**Table 1: Outcome Measures**

Construct	Measure(s)	Timing	Source
OUTCOMES			
Stool Frequency	Single integer count	Daily	N-of-1 App
Stool Consistency	Bristol Stool Scale 	Daily	N-of-1 App
Pain Interference	PROMIS® Pain Interference 	Weekly	N-of-1 App
IBD Severity	PROMIS® Gastrointestinal (GI) Symptoms*	Weekly	N-of-1 App
Growth	Weight †	Weekly	N-of-1 App
Self-Report Disease Activity	Pediatric Ulcerative Colitis Activity Index (PUCAI)  Short Crohn's Disease Activity Index (sCDAI) 	Weekly	N-of-1 App
Intestinal Inflammation	FecalCalprotectin	Baseline and at the end of each treatment period	Lab
Disease Activity	sPCDAI  , PUCAI 	Sporadic, Clinic Visits	Registry
MEDIATORS			
Psychological Well-being (Parent)	PROMIS® Anxiety PROMIS® Depression	Baseline	Web-survey or N-of-1 App
Psychological Well-being(Child)	PROMIS® Anxiety PROMIS® Depression	Baseline	Web-survey or N-of-1 App
Expectations of Benefit	Treatment expectations and preferences (adapted from published study) 	Baseline	Web-survey or N-of-1 App

\*Measure was validated in a sample of 1,007 children and youth in ICN ages 8-24. The scale exhibits acceptable internal consistency with a Cronbach's alpha of 0.74. The measure is highly responsive to differences in clinical status as assessed by both the patient and their physician/advanced practice care provider using validated measures and produces reliable estimates of GI symptom T-Scores ranging from 45 to 80.

†Optional, only if home scale available

### **3.5 Participant Selection and Withdrawal**

From ICN, we will recruit up to 60 patients with IBD and their families (primary caregivers) whose treatment decisions may be informed by the results of this study as determined by their GI care team. We will not exclude patients based on sex or race/ethnicity. We intend to enroll evenly across ICN centers, but will allow for fewer or more participants per site based on numbers of eligible patients and success with recruitment.

#### **3.5.1 Inclusion Criteria**

- Diagnosis of CD or UC or Indeterminate colitis (IC)
- Age 7-18 years
- Enrolled in the ImproveCareNow ICN2 registry; and

- Evidence of acute inflammation and/or elevated acute phase reactant as measured by Fecal calprotectin 1.5 times the upper limit of normal, Lactoferrin 1.5 times the upper limit of normal, CRP 1.15 times the upper limit of normal, or ESR 1.15 times the upper limit of normal (based on local reference ranges) obtained within 8 weeks of enrollment.
  - Potential participants who are close to meeting one of the acute inflammation and/or elevated acute phase reactant markers and who meet all other study criteria will be considered for study participation on a case by case basis by the investigative study team in consultation with the patient's primary gastroenterologist.

### 3.5.2 Exclusion Criteria

Complex and Unstable IBD:

- Currently or within the past 9 months has had an abscess, fistula, stricturing CD, or ostomy
- Ever had history of full colectomy
- Severe disease activity as measured by a short Pediatric Crohn's Disease Activity Index (SPCDAI) score of >45 or Pediatric Ulcerative Colitis Activity Index (PUCAI) score of >60 assessed within 3 weeks of enrollment
- Hospitalization or surgery planned within 3 months
- Ongoing active gastrointestinal infection
- Severe Malnutrition (BMI less than 5th percentile)
- Recent medication changes including:
  - Thiopurines, natalizumab, or methotrexate started within 8 weeks prior to enrollment
  - Anti TNF (infliximab, adalimumab) started within 8 weeks prior to enrollment
  - Vedolizumab started within 16 weeks prior to enrollment
  - Increase in corticosteroids within 4 weeks of enrollment or have dose >20 mg prednisone or equivalent

Evidence of Other Complicating Medical Issues:

- Other serious medical conditions, such as neurological, liver, kidney, or systemic disease
- Serious psychological or psychiatric conditions such as eating disorders or self-harm
- Pregnancy
- Tobacco, alcohol, or illicit drug abuse

Inability to Complete the Protocol

- Non-English speaking participants will be excluded because the mobile app only supports English speakers. The study timeline and funding prohibits development of a bi-lingual app.
- On SCD or modified SCD anytime within 8 weeks of enrollment
  - If an otherwise eligible patient is on SCD or modified SCD within 8 weeks of enrollment but they are noncompliant per the determination of the patient's dietitian/primary gastroenterologist, then this patient is eligible to participate in the study.

- Participants on a vegan diet will be excluded as the added restrictions of the SCD (on top of a vegan diet) would not provide these participants with the essential nutrients needed for a healthy diet
- Lack of smart phone and data plan for participating caregiver
- Participating in another interventional study

### **3.5.3 Participant Pre-screening and Recruitment**

We will recruit patients from participating ICN clinical sites. To introduce the study and provide information about dietary management for IBD/SCD, participating ICN clinics will mail a study flyer (Appendix J) to clinic patients prior to their upcoming appointment, call them by phone, and/or approach them at their clinic visit. Additionally, the study flyer will be available on various social media platforms. There will also be a study poster available for participating ICN clinics for use in advertising the study to potential participants (Appendix O). For those families who may be interested in a parent perspective of the SCD diet, a letter from our parent partners will be available (see Appendix P). Potential participants will also be informed about the study opportunity via several established channels within the ICN network, including monthly newsletters and blogs. In addition, we hope to make a short, animated video that will be used to recruit patients. The script for the video is attached as an Appendix B. As with our other patient-facing materials, since the study is pragmatic and minimal risk, we request to use this script as a template. It may have minor edits to the script which would not require IRB approval. Eligible participants will be identified through the standardized ICN pre-visit planning process. The site principal investigator will verify eligibility at the clinic visit. Study participants will enroll in the trial with their clinical team at a regularly scheduled clinic visit or at another visit within 2 weeks of a regularly scheduled visit if more convenient for the participant. Local clinic research coordinators will maintain a screening log in REDCap to track those that are screened, those who are excluded (and for what reasons), those that decline, and those who have enrolled. Most ICN clinic sites have obtained HIPAA waivers that allow study coordinators to identify potential study participants, evaluate patients for study eligibility at pre-visit planning meetings, and discuss participation in studies prior to consent being signed. For those who decide to participate, informed consent (and assent where applicable) will be obtained prior to initiation of study procedures.

### **3.5.4 Early Withdrawal of Participants**

If a patient experiences symptom flare, leading to either the diet intervention being stopped, medication being changed, or the need for surgical intervention, their participation in the N-of-1 protocol will be discontinued. In addition, patients who become pregnant during the study will be automatically withdrawn, as will patients that have  $\geq 7.5\%$  nonintentional weight loss. Patients may also withdraw if they feel that they are unable or unwilling to continue the assigned diet or data collection. Participants will be dropped from the study if they have a symptom tracking response rate of  $<50\%$  in the baseline period that does not improve after reasonable attempts by research coordinators (as outlined in the study SOPs) to assist participants in improving data collection. Because completion of stool fecal calprotectin is required to advance from one treatment period to another, a participant who never collects and sends in a stool specimen will be dropped at that point in the study. All data from such participants will be retained and analyzed. Patients who wish to terminate a treatment period early (and switch to the next assigned treatment) will not be considered withdrawals. Participants who wish to end their study participation early, but have completed at least two full diet treatment periods (i.e., A1 and B1), will have the option to discontinue participation and terminate the protocol early. Participants who choose to discontinue from the study in these instances will schedule a time to come into clinic to

receive their final study results and complete the end of survey questionnaire regarding their N-of-1 experience. These participants will not be considered withdrawals.

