Symptom tracking: Participants will use the Eureka N-of-1 mobile app to execute the N-of-1 protocol, track treatment periods, and track daily and weekly symptoms and disease activity. Participants and their clinician will be able to visualize the tracked data in real-time via the Eureka N-of-1 app and on the web portal. Parents of participants will always track symptoms using the mobile app. Patients  $\geq 14$  to 18 years will have the option of tracking for themselves (in addition to their parent). Patients  $< 14$  years will have parents track for them with child input. The questions to assess symptom and disease activity metrics are included in Appendix D. Participants will be asked to start tracking at the baseline visit. Patients will be asked to complete a minimum of 2 weeks of symptom tracking in the baseline period (14 daily measures, 3 weekly measures) and will be asked to continue with tracking once they initiate the N-of-1 Trial via the Eureka app.

Stool Collection: Participants will collect a home-based stool sample for fecal calprotectin analysis and biobanking for future analysis during the baseline period and the end of each treatment period. Stool specimens will be accepted as early as up to 2 weeks before the end of the treatment periods. Active participants will not be able to advance to their next treatment block until stool is collected and sent. If a patient elects to terminate a treatment condition early, they will be asked to submit a stool specimen at that time, prior to changing treatment conditions. Participants who discontinue the study after the first crossover (e.g., completion of baseline, Diet A1, and Diet B1) and terminate the protocol early may advance to the end of the study without additional stool collection. Patient instructions for stool collection are documented in Appendix E. Fecal

## USING SINGLE SUBJECT (N-OF-1) DESIGNS TO ANSWER PATIENT-IDENTIFIED RESEARCH QUESTIONS – AIM 1

calprotectin results will be made available to the clinicians as the results are returned from the lab.

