**Missing data:** Based on our experience, the overall completion rates of daily symptom trackers and weekly surveys by ICN patients and parents is >80%, we have found that when participants are working on a specific test or personal experiment with their physician, adherence increases to >90%. In cases of missing outcome data, we will ignore the missing values in the analysis of individual N-of-1 trials which is equivalent to treating them as being missed at random since the analysis is not adjusted for covariates. In the meta-analysis, we will explore the association of missingness with observed variables and condition analyses on these variables as appropriate. We will also explore treating the missing observations as latent parameters and estimate them as part of the Bayesian model assuming them to be missing at random. If patients decide to stop a treatment before 8 weeks, we will analyze the data available. Since effect modifiers in the meta-analysis are collected at the patient level, we expect them to be completely collected (e.g., there will not be a need for a statistical approach to address missing data for these variables). In the meta-analysis, we will perform the following sensitivity analyses for different types of missing data:

(1) analysis of all available data; (2) analysis excluding patients who withdrew early from the trial; (3) analysis of patients who completed the entire protocol, i.e. excluding those who withdrew early and those who terminated any treatment periods early.

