### **3.7 Safety and Adverse Events (AE)**

#### **3.7.1 AEs**

Clinical adverse events (AEs) will be monitored throughout the study. Since the study procedures are not greater than minimal risk, significant AEs are not expected. Potential AE's could include allergic reaction to a component of the diet, significant intolerance of the diet other than as an allergic reaction, and/or unintentional weight loss of  $\geq 5\%$ .

Expected adverse events include:

- Mild to moderate increase in abdominal pain, diarrhea, gas/bloating within the first 3-4 weeks of starting the new diet
- Weight loss of less than 5% in the first 3-4 weeks of starting the new diet
- Worsening of IBD due to failure of the diet to improve the disease. This could be manifested as new onset or worsened, bloody stools, diarrhea, abdominal pain, fistula, abscess, or bowel obstruction
- Hospitalization or surgery due to failure of the diet to improve the disease

Serious adverse events are not expected. However, if an SAE occurs and is determined to be possibly or definitely related to study treatment, it will be reported in accordance with CCHMC's IRB SOPs (as described in Section 3.7.2).

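### No stool specimen is requested when a flare ends participation, so a flare before about week 6 leaves no planned fecal calprotectin value for the period that failed

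*Combined protocol and SAP*

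**What the plan says.** Section 3.3.1 sets four alternating 8-week periods. The Outcome Measures text in section 3.4 makes FCP a primary outcome and the central marker of intestinal inflammation. Table 1 schedules it at baseline and at the end of each period.

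Section 3.4, Stool Collection, has three rules that matter here:

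- Timing: "Stool specimens will be accepted as early as up to 2 weeks before the end of the treatment periods".
- Early switch: "If a patient elects to terminate a treatment condition early, they will be asked to submit a stool specimen at that time". The sentence goes on to place this before the change of condition.
- Stopping after the first crossover: such participants "may advance to the end of the study without additional stool collection".

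Section 3.5.4 treats a flare separately. "If a patient experiences symptom flare, leading to either the diet intervention being stopped, medication being changed, or the need for surgical intervention", participation is discontinued. No specimen is mentioned. The same section keeps and analyzes the data of those who leave, and says that early switchers are not withdrawals.

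Section 3.7.1 expects such cases, listing among expected adverse events "Worsening of IBD due to failure of the diet to improve the disease".

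On missing data, section 3.6.2 says of the individual trials that "we will ignore the missing values in the analysis of individual N-of-1 trials which is equivalent to treating them as being missed at random". For the meta-analysis it will "explore the association of missingness with observed variables and condition analyses on these variables as appropriate", and a further step is to "explore treating the missing observations as latent parameters and estimate them as part of the Bayesian model assuming them to be missing at random". The planned sensitivity analyses use all available data, drop early withdrawals, or keep full completers only.

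**The concern.** The protocol recognizes that a diet stopped early needs a specimen at the time of stopping, but writes that rule only for the patient who moves on to the next diet. The child for whom the diet appears to have failed leaves without one. FCP is then missing because of the course of the disease, which is the situation that a missing-at-random analysis handles worst. None of the three sensitivity analyses can supply the absent value.

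The individual result is at stake first, since section 3.6.1 names the individual treatment decision as the primary goal. After a flare in period 2 there is no FCP comparison of the two diets. After one in period 3 or 4, the failed diet is represented only by its earlier, pre-flare value. At population level, the diet with more flares could look closer to the other on FCP than it is. It is also unclear whether the post-crossover stool waiver covers flare exits.

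**Working it through.** **When the window opens.** 8 weeks - 2 weeks = week 6. A flare exit before then leaves no planned value for that period.

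**FCP values left after such an exit** (failed diet / other diet):

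| Flare in | As written | With exit specimen |
|---|---|---|
| Period 1 | 0 / 0 | 1 / 0 |
| Period 2 | 0 / 1 | 1 / 1 |
| Period 3 | 1 / 1 | 2 / 1 |
| Period 4 | 1 / 2 | 2 / 2 |

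The specimen restores a between-diet contrast only for period 2. For period 1 it gives a value on the failed diet but no contrast. For periods 3 and 4 it adds the flare value to an earlier one.

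**Assumptions.** N = 60 is from section 3.6.1. The documents give no flare rate, flare timing or FCP rise. Assumed: flare probability f = 5, 10 or 20% per period; share discontinued r = 0.5 or 1 (the rest switch, with a specimen); flares spread evenly over weeks 2-8, so w = 5/7 fall before the window; FCP 2, 3 or 5 times higher at a flare. Write g = f x r.

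**Children affected.**

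- Failed-period value lost: 60 x w x (1 - (1 - g)^4) = 4.1, 7.9, 14.7 (r = 0.5) and 7.9, 14.7, 25.3 (r = 1).
- Flare in period 2: 60 x w x g x (1 - g) = 1.0 (g = 0.025) to 6.9 (g = 0.2).
- Flare in period 3 or 4: 2.0 to 9.9, which is 49% (2.0/4.1) down to 39% (9.9/25.3) of the lost values. The other 51-61% fall in periods 1-2.
- The top case is an upper bound: at g = 0.2, 1 - 0.8^4 = 59% of children would be discontinued.

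A constant flare hazard over 32 weeks, with total flare risk of 5-50%, puts 51-59% of pre-week-6 flares in periods 1-2.

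**Individual result after a period 4 flare.** Take log FCP with within-child SD 0.7 and no diet effect other than the flare. With the specimen there are two values per diet. If d is the difference in mean log FCP (failed minus other) and s the pooled SD on 2 df, the posterior probability under a 1/sigma prior that the failed diet is better is T2(-d / (s x sqrt(1/2 + 1/2))). Averaged over simulated children this is 0.38, 0.32 and 0.28 at multiples 2, 3 and 5 (0.25-0.41 for SDs of 0.5-1.0). Without the specimen, one value against two on 1 df averages 0.50.

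**Population.** Simulated ABAB/BABA children were analyzed by random-intercept GLS of log FCP with period effects (between-child SD 1.0, within-child SD 0.7). Shift toward no difference with all flares discontinued:

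| Flare rates | x2 | x3 | x5 |
|---|---|---|---|
| 5 v 10% | 0.026 | 0.042 | 0.061 |
| 5 v 15% | 0.052 | 0.082 | 0.120 |
| 10 v 20% | 0.050 | 0.079 | 0.117 |

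The standard error at N = 60 is 0.099-0.110, so this is 0.3-1.2 standard errors. With half discontinued the shift is 0.01-0.06, starting near 0.1 standard errors. At 8 v 10% with all discontinued it is 0.01-0.02; at equal rates it is zero. With the specimen and all discontinued, 0.01-0.04 remains.

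Worked case, 5 v 15% and threefold: the flare-driven difference is 0.10 x ln 3 = 0.110, and 0.082/0.110 = 75% of it is lost. With the specimen 25% is lost.

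**The case against.** The strongest case is that the consequences are mostly assumed and partly covered.

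- **Bias needs unequal flare rates.** The two diets are closely related, and nothing in the documents suggests a 2- to 3-fold difference. This stands and limits the population claim.
- **Other routes to the value.** The Outcome Measures text allows missing measures to be taken from other sources, and clinic visits occur as needed, so a clinically ordered FCP may be retrieved. That stands, but nothing schedules one.
- **Conditioning on observed data.** In the 5 v 15%, threefold case, adjusting for a symptom score (within-child SD 5) leaves 74% of the flare-driven part lost if symptoms and FCP are uncorrelated and the flare shift is 5 points; 53% at correlation 0.3 and 10 points; and 18% at 0.6 and 15 points. The last is better than the specimen's 25%. Adjustment may therefore suffice, but only if symptoms track FCP closely, and it is planned only for the meta-analysis.
- **The specimen is imperfect.** Section 3.3.1 expects inflammation markers to respond by 2 months, so a sample at weeks 2-5 of periods 2-4 may partly reflect the previous diet. The simulation credits the whole rise to the current diet. This stands, but the protocol already accepts it for early switchers.
- **Reading and unseen documents.** A flare stop might be called elective, but the specimen rule is tied to changing condition, whereas a flare ends participation. The SOPs, Appendix E (stool instructions) and the formal SAP were not available and could contain a request.

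A reader might infer that a flare exit usually leaves no FCP at all for the failed diet. The documents do not support that: in periods 3-4, which hold 39-49% of the lost values, an earlier value exists. A reader might also extend the 50% comparison to period 3 flares. Without the specimen, such a child has one value per diet and no replicate, so there is no comparable probability, and section 3.6.2 gives results only where the data allow a valid analysis.

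**Conclusion.** The gap is real in the text supplied. A flare exit before about week 6 has no planned FCP for the failed period, and none for the diet if this was its first exposure. The loss is caused by worsening and is then ignored or treated as missing at random.

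Its size is modest and rests on assumed flare rates, timing and FCP rises: about 4-25 of 60 children lose the value, of whom 1-7 flare in period 2 and lose a contrast that the specimen would give. For a period 4 flare, the chance that the failed diet is better on FCP averages 50% without the specimen and 28-38% with it. The population log FCP ratio moves toward no difference by about 0.01-0.12 (0.1-1.2 standard errors) if flare rates differ 2- to 3-fold, and by little or nothing if they are similar.

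It would go too far to infer that the diet comparison as a whole is biased. The population shift concerns FCP only, diet against diet, and only its flare-driven part. Symptom outcomes are recorded up to the flare and are hardly affected. The change is still worth making, because the value cannot be recovered once treatment changes.

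**What to change.** - **Sections 3.4 and 3.5.4:** request a stool specimen when a flare ends a diet period, before new medication or a change of diet where this does not delay care. State that the post-crossover waiver does not apply to flare exits.
- **Section 3.6.2:** use that specimen as the period's FCP value, and tabulate flare-ended periods with and without FCP, by diet.

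The cost is about one sentence in each section, one table, and roughly 4-25 home specimens at the assumed rates, within the one per period already planned. The downsides are a small burden on an unwell child and a value that reflects less than 8 weeks on the diet. If the SOPs or Appendix E already request the specimen, the change reduces to saying so in the protocol.

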### 3.3.3 Interventions and Comparators

The diets are defined as follows:

1. Usual Diet (Baseline Condition): Patient eats a typical, non-SCD, diet. Diet may include some restrictions (which is common in IBD) such as seeds/nuts or gluten, but exclusions will not be as broad as with the SCD and Modified SCD (e.g., patient still eating grains and/or dairy). May include full or partial exclusive enteral nutrition as the currently available liquid supplements are not SCD compatible.
2. Specific Carbohydrate Diet (SCD): The dietary program will follow recommendations outlined in *Breaking the Vicious Cycle* by Elaine Gottschall. Allowed foods include meat/fish/poultry, eggs, some legumes (e.g., lentils and split peas are permitted, chickpeas and soybeans are not), fully fermented yogurt, non-starchy vegetables, ripe fruit, nuts/seeds, honey and nut flours (e.g. almond flour or coconut flour). SCD compatible vitamins are allowed and will be recommended on as needed basis by study dietitians. Restricted foods include all grains, milk

products aside from 24-hour fermented SCD yogurt and cheeses aged greater than 30 days, starchy vegetables, processed foods with food additives and sweeteners other than honey.

3. **Modified Specific Carbohydrate Diet (SCD):** A more liberal, and thus, perhaps more sustainable version of the SCD. In addition to the foods in the SCD, allowed foods will expand to include organic rice, oats, sweet potatoes, Grade A maple syrup and 100% unsweetened cocoa powder (not Dutch processed) or 100% cacao powder, nibs, or butter (no sugar added) for this group. For oats, organic rice, and sweet potatoes, patients will be instructed to consume a minimum of 3 servings and a maximum of 6 servings of any combination of these items per week. On any given day, they should not have more than 2 servings of any combination of these items. A serving size is 1 cup. For maple syrup and 100% unsweetened cocoa powder (not Dutch processed) or 100% cacao powder, nibs, or butter (no sugar added), patients will be asked to consume a minimum of 2 Tablespoons of each item per week and a maximum of  $\frac{1}{2}$  cup of each per week. The reasons for the minimum amount of these food items each week is to distinguish the diet from the SCD enough to provide a useful comparison. Gluten, corn products, milk products (except yogurt and aged cheeses), sweeteners (except honey), and process foods will still be restricted.

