Follow Up contact: Based on standard of care for initiating a new dietary treatment, patients will be evaluated by the dietitian and/or physician or advanced practice care provider (i.e., nurse practitioner or physician's assistant) at  $2 \pm 1$  weeks after starting each new diet. This visit may be completed by phone call, video call or telemedicine visit, per the discretion of the primary GI physician or advanced care provider. If this appointment does not take place in-clinic, it is the site's research staff's responsibility to make sure that the patient's weight is obtained using the same scale at every weigh in and that the patient reports the measured weight to the study staff. Participants will also have a phone or in-person follow-up with either their site's dietitian or the site coordinating center dietitian in each treatment period. The dietitian will evaluate patient weight (on clinic scale at follow up visits and if available by home scale) and nutritional intake. S/he will prescribe SCD compatible nutritional supplements as needed based on review of the diet recall. In addition, at the clinic visits, follow up phone calls or visits, and during any other patient contact, the dietitian will carry out standard of care activities including, but not limited to, evaluating the participant's nutrition and overall health, assessing the participants nutritional and dietary needs, providing diet advice, sharing sample meal plans, developing new meal plans, and sharing recipes from books, online resources, or other personal sources. In the event that the site dietitian is unavailable for follow-up contact, these visits may be conducted by the site coordinating center dietitian via video call (i.e., Zoom, Skype) if permission is granted by the patient's primary GI physician or advanced care provider.

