**Clinical Evaluations:** Participants will be seen for clinic visits as needed throughout the study. Based on standard of care for initiating a new dietary intervention and the fact that patients enrolled in this study have mild or moderate disease activity, close follow up is recommended. Participants will have a follow up visit  $8 \pm 2$  weeks from initiation of the first diet period and then as needed over the remainder of the study, with timing based on each individual center's standard practice and patient need. This pragmatic design allows us to test the use of the N-of-1 methodology for diet intervention as it would be delivered in regular clinical care. Data collected at routine clinic visits is standardized and includes weight, height, current medications, laboratory assessment, and disease activity (PUCAI and SPCDAI). This data is entered in the ICN registry. Assessment of Vitamin D levels is performed per local site standard of care. This data is not collected in the ICN registry. The date and results of all Vitamin D levels collected at regular clinical evaluations will be entered in the REDCap database by the research coordinator or dietitian at each site.

[figure not shown]

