## Outcome Measures

Study outcomes and mediating factors are detailed in Table 1. Primary outcomes across all patients will include patient reported outcomes (PROs) of stool frequency, stool consistency, pain interference and GI symptom severity (see Appendix D), and fecal calprotectin. Secondary outcomes will include patient-reported disease activity scores as measured by the Pediatric Ulcerative Colitis Activity Index (PUCAI) and Short Crohn's Disease Activity Index (SCDAI), clinically-evaluated disease activity scores contained in ICN registry (PUCAI and sPCDAI), growth, laboratory markers of inflammation and disease status [C Reactive Protein (CRP), Hematocrit, Erythrocyte Sedimentation Rate (ESR), Albumin]. Fecal calprotectin was selected as the central marker of intestinal inflammation because it correlates well with both clinical and histologic remission, is noninvasive and objective, and has been shown to be a useful tool to monitor response to therapy. Safety Outcomes: The major safety concerns for patients with IBD participating in a diet intervention include weight loss and inadequate nutrition. Weight loss typically occurs within the first few weeks of starting the diet. Weight will be assessed at all clinic visits and at the dietitian follow up visits (weeks 4 and 12) and by weekly weights entered in the Eureka app if there is a home scale available. If a home scale is available, patients will be instructed to obtain an initial weight on their home scale at the beginning of the baseline period and use the same home weighing scale throughout the study period. Nutrition intake will be monitored by the dietitian regularly for all enrolled patients and will be assessed via 3-day diet diaries conducted at specified intervals (baseline and in weeks 3-5 of each treatment period) and weekly weight tracking (if available). In addition, we will collect results of any serum Vitamin D level monitoring conducted as part of routine care and will report these results to the DSMB. Mediating factors: We will collect demographic data from the ICN registry including age, gender,

## USING SINGLE SUBJECT (N-OF-1) DESIGNS TO ANSWER PATIENT-IDENTIFIED RESEARCH QUESTIONS – AIM 1

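### The automatic 7.5% weight-loss withdrawal rule does not re-apply the BMI entry limit, so a child enrolled less than 8.1% above that limit can fall below it without triggering the rule

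*Combined protocol and SAP*

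**What the plan says.** Section 3.5.2 lists among the exclusions "Severe Malnutrition (BMI less than" the 5th percentile. It is an entry criterion only.

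Section 3.5.4 sets the rule that applies once a child is on the diet: "patients who become pregnant during the study will be automatically withdrawn, as will patients that have" a loss at or above 7.5%. The text that follows the percentage is "nonintentional weight loss. Patients may also withdraw if they feel that they are unable or unwilling", so the rule does not say from which weight, over what time or on which scale the loss is measured. It contains no BMI criterion.

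Section 3.7.1 treats smaller losses in two ways. It lists as an expected event "Weight loss of less than 5% in the first 3-4 weeks of starting the new diet", and it names unintentional loss of 5% or more as a potential adverse event. Neither item names a reference weight or attaches a BMI check.

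Section 3.4 supplies the monitoring. A visit about two weeks into each new diet includes a weight, and there is a further dietitian contact in every period. A 3-day diary is analysed for nutrients in each period, and the dietitian may "prescribe SCD compatible nutritional supplements as needed based on review of the diet recall". On clinic visits the section says: "Data collected at routine clinic visits is standardized and includes weight, height, current medications, laboratory assessment, and disease activity". The outcome text in the same section names weight loss and inadequate nutrition as the major safety concerns.

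**The concern.** The entry criterion and the main hazard of the intervention are the same thing. The protocol judges a child below the 5th percentile too malnourished to start a restrictive diet. If a child reaches that BMI while on the diet, no stated rule requires anyone to stop it or even to record a decision. A percentage-loss rule gives least protection to the children with least reserve: the closer a child starts to the cut-off, the smaller the loss needed to cross it, while the trigger stays at 7.5%.

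The participants are 7 to 18 years old and are followed for at least 34 weeks, so some will grow. A growing child whose weight merely stands still loses BMI with no weight loss at all, and a rule written in weight loss cannot register that.

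**Working it through.** The plan states no derived figure on this point, so there is nothing to reproduce first.

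**Inputs from the documents**
- Entry cut-off: BMI at the 5th percentile, called P5 here (3.5.2).
- Withdrawal at nonintentional loss of 7.5% or more (3.5.4).
- Adverse-event line at unintentional loss of 5% (3.7.1).

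**Assumptions for the main result:** height and P5 stay constant, and loss is measured from enrolment weight.

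**Formula.** At constant height BMI is proportional to weight. A child enrolled at BMI = k x P5 who loses a fraction L of weight has BMI = k(1 - L) x P5. This is below P5 exactly when k < 1/(1 - L).
- L just under 7.5%: k < 1/0.925 = 1.0811, a margin of 8.1% above P5.
- L just under 5%: k < 1/0.95 = 1.0526, a margin of 5.3%.

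**Loss that brings a child to P5** (1 - 1/k):

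| Enrolled above P5 | Loss that reaches P5 | 7.5% rule met? |
|---|---|---|
| 2% | 1.96% | no |
| 4% | 3.85% | no |
| 6% | 5.66% | no |
| 8% | 7.41% | no |
| 9% | 8.26% | yes, rule acts first |

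**Sensitivity to growth** (assumed gains; the documents give none). With a fractional height gain g and P5 unchanged, the margin becomes (1 + g)^2/0.925 - 1:
- g = 1%: 10.3%
- g = 2%: 12.5%
- g = 3%: 14.7%

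If height is constant but P5 itself rises by 1% or 2% as the child ages, the margin is 1.01/0.925 - 1 = 9.2% or 1.02/0.925 - 1 = 10.3%.

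**Sensitivity to the reference weight** (extreme bound). If the reference were reset at each diet period, a loss just under 7.5% in every period would never trigger the rule. The cumulative loss would be 1 - 0.925^2 = 14.4% after two periods and 1 - 0.925^4 = 26.8% after four.

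The 8.1% comes from the missing BMI limit alone. The unnamed reference weight is a separate ambiguity that can only widen the gap.

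**The case against.** The strongest reply is that an entry criterion is not a stopping rule. Section 3.5.2 also excludes severe disease activity by score, and 3.5.4 does not re-apply those scores; it uses an event rule for flares. A percentage rule for nutrition follows the same pattern. The risk is also watched: weights early in each diet period, dietitian contacts, diary analysis, weekly home weights where a scale exists, reporting of adverse events to the coordinating center, and DSMB review. A treating team can stop the diet at any time.

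Most of this stands and lowers the urgency. It does not close the gap, because none of these steps states a BMI at which someone must act. The protocol did choose an automatic rule for this hazard.

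A reader might infer more than the documents support:
- *That every child less than 5.3% above the cut-off will fall below it through expected loss.* The expected event is any loss under 5%. Only a loss large enough for that child's own margin crosses the cut-off.
- *That the 8.1% holds whatever the reference weight.* It assumes loss from enrolment.
- *That such a child would stay on the diet to the end.* This supposes that the clinical team does not act and that no further loss occurs, since further loss brings the 7.5% rule into play.
- *That weight is checked only early in the study.* The outcome text says "Weight will be assessed at all clinic visits and at the dietitian follow up visits (weeks 4 and 12", but the follow-up text in 3.4 plans weights after each new diet. The shorter list is an incomplete summary.
- *That children on formula lose all nutritional support.* Section 3.3.3 says of the usual diet: "May include full or partial exclusive enteral nutrition as the currently available liquid supplements are not SCD compatible". Section 3.4 nevertheless provides for compatible supplements and meal planning. This is a side issue.

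**Conclusion.** The point holds as a cheap safety improvement. Followed exactly, the withdrawal rule lets a child enter the range that the protocol itself calls severe malnutrition, on a diet whose named hazard is weight loss, with no required action.

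The band is up to 8.1% above the cut-off for the withdrawal rule and up to 5.3% for the adverse-event line, given constant height, an unchanged cut-off and loss measured from enrolment weight. Relaxing these assumptions through height growth, a rising cut-off or a reference weight reset each period enlarges the band.

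The number of children affected cannot be computed. The documents give neither the BMI distribution of those enrolled nor the weight loss to be expected in each, so any count out of 60 would rest on invented inputs. The study SOPs and the DSMB charter are separate documents that were not available, and they may already contain a limit or name the reference weight.

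**What to change.** Add to 3.5.4: *If BMI falls below the 5th percentile for age and sex (weight at any planned contact, most recent measured height), the diet is stopped unless the site PI documents a decision to continue.* State there and in 3.7.1 that the 5% and 7.5% thresholds are measured from enrolment weight on the same scale.

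The cost is small. Weights are already planned in every diet period and heights are recorded at clinic visits, so no visit or measurement is added. The outcomes and the sample size do not change.

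There are two downsides. A few children enrolled just above the cut-off will need an extra review or will stop early, some after small losses: a child 2% above would meet the trigger at a loss of about 2%. And the height used may be some months old, because after the visit at about week 8 clinic visits are only as needed until completion. The check may therefore miss part of the growth effect.
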